3 OBJECTIVES AND ENDPOINTS

3.1 OBJECTIVE

The objective of this study is to demonstrate the safety and performance of the Marani Fetal Monitoring Telehealth System (M•care™ System) for use in antenatal monitoring of pregnant women \geq 32 weeks' gestation. The M•care System will be evaluated by comparing Fetal Heart Rate (FHR), Maternal Heart Rate (MHR) and Uterine Contractions (UC) to Doppler FHR, Pulse Oximeter MHR, and tocodynamometer (TOCO) UC, respectively, measured with an FDA cleared standard of care cardiotocography (CTG) device.

3.2 PRIMARY PERFORMANCE MEASURES

- 1) M•wrap FHR limit of agreement (LOA) within the performance goal of 15 beats per minute (bpm) of FHR measured with CTG
- 2) M•care MHR limit of agreement (LOA) within the performance goal of 10 beats per minute (bpm) of MHR measured with CTG

3.3 SECONDARY PERFORMANCE MEASURES

The secondary performance measure is Uterine Contractions (UC) sensitivity as measured by the M•care System versus the standard of care CTG device, with a performance goal of greater than or equal to 80% agreement. Sensitivity is defined as the proportion of UC events identified by standard of care that are simultaneously (e.g., within 30 seconds) identified by the M•care System.

Hypothesis testing for UC sensitivity will only be conducted if the primary performance measures (i.e., equivalence in FHR and MHR) are met.

Additional UC endpoints as measured by the M•care System verses standard of care CTG device include:

- 1) Positive predictive value (PPV) defined as the proportion of UC events identified by both the M•care System and standard of care out of those that are identified by the M•care System
- 2) False Positive Rate defined as the proportion of UC events identified by the M•care System that are not identified by the standard of care

No hypothesis testing is planned for the PPV and false positive rate endpoints.

3.4 SAFETY ENDPOINT MEASURES

Incidence of device related and/or protocol procedure related adverse events (AEs) related to the study device, The Marani Health M•care System, in pregnant women with a singleton pregnancy ≥ 32 gestational weeks. Due to minimal risk, we do not expect any related serious events (see safety in section 8).

3.5 SUCCESS CRITERIA JUSTIFICATION

Fetal Heart Rate (FHR)

The primary performance endpoint is M•care FHR limit of agreement (LOA) within 15 beats per minute (bpm) of FHR measured with cardiotocography. This 15 bpm LOA is a clinically acceptable range to recognize common clinical phenomena including bradycardia, tachycardia, accelerations, and decelerations.⁷ Most FHR clinical phenomena are defined as an increase or decrease of 15 bpm from baseline, which could be detected given a 15-bpm limit of agreement. Clinical practice guidelines state that moderate FHR variability, between 5 and 25 bpm, is considered normal.¹¹ Baseline HR variability can range from 3-12 bpm as measured with standard CTG, and which increases with gestational age.^{7,12} Moreover, FHR calculations derived from CTG have previously been shown to have a high degree of inaccuracy when compared with those derived from fetal ECG-based measurements.⁷ Thus, given the known limitations of CTG, some of variability quantified by the limits of agreement in this study may be due to error in CTG measurements and not M•wrap measurements.

In a study reported by Cohen, et al, the limits of agreement for both FHR and MHR with FSE, abdominal fetal ECG and ultrasound were clinically evaluated.¹³ In this study, the abdominal fetal ECG limits of

agreement (± 1.96 SD) for fECG to FSE was 8.40; -8.72 and for the Doppler ultrasound technique the bias is significantly greater, -2.87, with limits of agreement of (22.65, -28.39)⁷ indicating an even wider interval may be considered clinically insignificant. The FHR performance goal interval of [-15, 15] bpm is based on the clinically significant margin for differences in FHR that have been variously reported in the literature as: >15bpm (e.g., large acceleration)¹⁴, and >25bpm (e.g., marked baseline variability).¹⁵

The mean difference (bias) between FHR measurements with fECG and Doppler methods has been reported as 0.74 bpm with 95% LOA of +/- 12 bpm (e.g., SD= 6.1 bpm) by Reinhard et al¹⁴, and -0.3 bpm with 95% LOA of (-8.84, 8.24) (e.g., SD=4.36) by Mhajna et al.¹ The Monica Health Novii wireless patch system Instructions for Use (107-PT-005-EN rev P) indicates that when comparing the Monica Novii System and the predicate Monica AN24 System, the 95% LOA was -13.7BPM to 14.1 BPM.

Maternal Heart Rate (MHR)

The primary performance endpoint is M•care MHR limit of agreement within 10 beats per minute (bpm) of MHR measured with Pulse Oximetry MHR with the CTG. It has been shown that a woman's heart rate increases by an average 10 to 20 bpm during pregnancy.¹⁶ The mean heart rate at 34-42 weeks' gestation was reported by Van Oppen et. Al as 92 ± 1 .¹⁷ Sherman, et. al showed that heart rate variability is 15.8 ± 1.8 during the latent phase and 12.7 ± 1.1 during the active phase of the first stages of labor.¹⁸ Other clinical studies have chosen an increase or decrease in heart rate of ≥ 10 beats per minute (bpm) at the peak of a contraction as compared to 10 seconds before the contraction to be regarded as either an acceleration or deceleration.¹⁹ As such, these reports support that a 10 bpm LOA is a clinically acceptable range to recognize common clinical phenomena including accelerations and decelerations. Additional considerations for tachycardia and bradycardia have been considered. Odendaal et al. reported that tachycardia is defined as a "rate of at least 100 beats per minute under resting conditions" while the definition of bradycardia in pregnancy "has not been standardized."²⁰

Uterine Contractions

Uterine contractions are identified based on the tracings output by the relevant device; knowledgeable readers interpret the tracings to identify the contractions. The outcomes are binary: either the event happened, or it did not. To evaluate the performance of this binary outcome, our success criterion is to obtain results consistent with cleared devices with similar technologies such as the Monica AN24 per K101801 510(k) Summary, Monica Novii Instructions for Use (107-PT-005-EN rev P), and TOCO¹³ in general.

4 STUDY DESIGN

4.1 OVERALL DESIGN

Hypothesis: We hypothesize that non-invasive electrical recordings will permit acquisition of the fetal ECG, maternal ECG and uterine contractions (UC) with proper signal processing and will ultimately support the development of an abdominal fetal monitor that is wireless and unobtrusive. This will be accomplished with the Marani M•wrap wearable garment.

This study is a prospective paired comparison, multi-site trial intended to establish the equivalence of the Marani M•care System with FDA-cleared Doppler FHR, TOCO UC and pulse Ox MHR reference. Subjects who are admitted to triage for potential labor or other inpatient evaluations including but not limited to evaluation for PROM, who are attending in-clinic appointments for Non-Stress Tests (NST), Contraction Stress Test (CST), or at the convenience of the subject will be monitored with both devices simultaneously for FHR, UC, and MHR. Only the data from the CTG device, the standard of care, will be available to the clinical team in a clinical setting. CTG information will not be interpreted in a non-clinic research visit setting. The M•care System data will be compared to that of the simultaneously obtained standard of care CTG data to determine equivalence after the monitoring is completed. No interim analysis is planned.

4.2 END OF STUDY DEFINITION

Subjects will complete this study Setup and Monitoring sessions in a single visit. Consenting and Screening may occur at a different time prior to Setup. Each individual subject study will be considered complete when **all** the following conditions have been met:

- Consenting process has been completed
- M•wrap monitoring is complete for that subject
- Transmission of subject data has been confirmed by Marani, and
- All study CRFs are finished.

The overall study will be considered complete when **all** the following conditions have been met:

- All subjects have completed their study visits as described above
- Data queries have been adjudicated
- Database is closed, and
- All sites have had their closeout monitoring visits and received their closeout confirmation letter.

5 STUDY POPULATION

5.1 INCLUSION CRITERIA

Subjects eligible for this clinical study must fulfill **all** the following criteria:

- 1) Able to provide Informed Consent and follow study instructions
- 2) 18 years of age or older
- 3) Pregnant subjects \geq 32 weeks' gestation
- 4) Singleton pregnancy
- 5) BMI ≥ 15 , pre-pregnancy
- 6) BMI ≤ 45 , pre-pregnancy
- 7) Belly circumference ≥ 80 cm and ≤ 135 cm

NOTE: Subjects admitted for induction of labor and subjects being monitored for premature rupture of membranes (PROM) or other inpatient evaluations can be enrolled in the trial.

5.2 EXCLUSION CRITERIA

Subjects are not eligible if **any** of the following criterion are met:

- 1) Known major fetal malformation or chromosome abnormality
- 2) Abdominal medical skin conditions, including surgical incisions, open wounds with or without infections, edema, or irritation
- 3) Subjects with implanted electronic devices (pacemakers, defibrillator, etc.)
- 4) Involvement in another clinical trial currently or previously in this pregnancy that, in the investigator's opinion, would affect the conduct of this study.
- 5) Medical or obstetric problem that in investigator's opinion would make the subject incapable of taking part in the study.
- 6) In the investigator's opinion, the subject is not likely to be available for the minimum 60 minutes of the monitoring session.
- 7) History of skin allergies to cosmetics and lotions.
- 8) Known allergies to silver, nylon, or polyester.

Note: some people with sensitivity to silver jewelry are sensitive to the impurities in silver alloys and not to silver itself.

5.3 SCREEN FAILURES

Consented screen failures are defined as subjects who consent to participate in the clinical trial but are not entered into the study due to unmet inclusion or exclusion criteria. A screen failure log will be maintained at each site.

5.4 STRATEGIES FOR RECRUITMENT

Recruitment will include pregnant women (≥ 32 weeks) who are coming to clinic for routine antenatal visits, scheduled research visits, or who are presenting for scheduled induction of labor, admitted for premature rupture of membranes (PROM) or other inpatient evaluations, in observation in labor triage. Visits will be scheduled at the convenience of the mother.

The study will enroll a minimum of 80 evaluable subjects. Two study groups will be included in order to ensure collection of sufficient uterine contraction activity data. The study groups are as follows:

- Antenatal – includes subjects evaluated per obstetric standard of care in the clinic/office environment and subjects completing research-only visits in a non-clinic setting with oversight by a healthcare professional. Subjects with premature rupture of membrane (PROM) will also be included.
- Enriched Hospital – includes subjects in early (latent) phase of labor with suspected or confirmed uterine contractions, subjects who are being induced for labor.

6 STUDY REGIMEN

6.1 STUDY ADMINISTRATION

The group of subjects enrolled into the study may include subjects scheduled for routine antenatal visits; participation in the study may be offered while in the office for their scheduled visit. Other eligible subjects may be recruited from the general population for a scheduled research visit in a non-clinical setting. Each subject may identify a time that works best for them. During the visit (subjects must be 32 weeks or greater), fECG, mECG signals and UC will be recorded. The aim is to record signals for up to 120 min. The definition of success is: (1) capture of signals with CTG and (2) validation that the M•wrap is capturing signals.

The sequential order for recording, based on our estimation of the likelihood of success, is as follows:

1. Apply the CTG doppler transducer and confirm the CTG doppler transducer is operating normally.
Remove the doppler transducer and put on M•wrap.
2. Utilize M•wrap + CTG (FHR, MHR, and UC) to collect data.

 MARANI	MARANI PRENATAL CONNECTED CARE (M•care) Safety and Effectiveness Study (M•CARE SE Study)
Protocol Number: MH-001	Revision Number: G

For purposes of recording signals, data will be collected from the subject simultaneously using both the M•wrap and CTG. Refer to Section 1.2 for the expected step-by-step Study Schema. The FHR will be located with the doppler transducer on the CTG. Once a strong FHR is located, prepare for and conduct placement of the appropriately sized M•wrap placement per the current Instructions for Use (IFU) Manual. With guidance from Marani, holes/openings will be created in the wrap fabric to allow for placement of the CTG transducers such that both devices can be used simultaneously. See Figure 3 for an example of wrap placement and use of the wrap with CTG transducers. Appendix 1 describes M•wrap configurations for concurrent CTG use in more detail. The black compression band will be placed over the M•wrap and the CTG transducers throughout simultaneous data collection (see Figure 4). Marani personnel will be present to perform necessary device modifications to allow for CTG placement and to initiate data collection from the M•care Mobile Application.

Based on the design of the M•care Mobile Application, each 60-to-120-minute Monitoring Session may include up to four data collection initiations from the M•care Mobile Application. The mother may get up and walk around between data collection sessions.

Figure 3. M•wrap with Example CTG Placement

[figure not shown]

Figure 4. Black Compression Band over M•wrap and CTG Transducers

Uterine contractions will be recorded using the standard external acquisition tocodynamometer system within the CTG, and the information synchronized to the recorded biopotential signals. These signals will be collected over a 60-120 min period.

Figure 5 depicts the connectivity of the Marani M•care System. The M•wrap signal will stream via Bluetooth through the M•core to a Marani-provided mobile phone containing either Android or iOS operating system and then to a secure Marani server (utilizing Amazon Web Services). The CTG signals labeled only with Subject ID will be extracted from a MIB / RS232 port on the CTG machine and captured on a Marani-provided laptop for analysis and comparison to the M•wrap data. A Medicollector Cable CBL-5010 will be used to connect the CTG to the Marani-provided laptop. For the purpose of this study, the

Confidential

Refer to QMS Number: VAL-PRO-20-0004, Rev G

DCR-00306, Effective – 14-Dec-2022

subject-facing mobile application will be controlled by Marani. Site specific procedures will be followed for information security.

[figure not shown]

Figure 5. Marani M•care System

Study subjects may be asked to be photographed to demonstrate where the electrodes are meeting the subject's abdomen, and possibly for publication. Photographs will only include abdominal pictures of the M•wrap; no identifying photos of faces will be included.

Study garments and cores will be reused across subjects. Cleaning procedures to allow for reuse of garments are in accordance with FDA and CDC guidelines for non-critical subject care items. Applicable references include FDA's 2015 Guidance "*Reprocessing Medical Device in Health Care Settings; Validation Methods and Labeling*" and CDC's 2008 Guideline document, "*Guideline for Disinfection and Sterilization in Healthcare Facilities*."

6.2 ACCOUNTABILITY

6.2.1 ACQUISITION AND ACCOUNTABILITY

An adequate number of M•wrap and M•core devices will be supplied to each study site prior to initiating the study and may be resupplied as needed. Each shipment of device supplies for the study will contain a shipment form to assist in maintaining current and accurate inventory records. When a device shipment is received, the investigator/coordinator will acknowledge receipt.

Accountability records will be maintained at the site at all times. The identification number of the subject, the date, lot number, expiration date of the M•wrap dispensed, and the date and quantity of devices returned will be recorded. The devices will be noted on the appropriate inventory forms. Per Marani Health or Marani Health designee visit at the site, accountability of the returned devices should be performed and recorded.

Upon conclusion of the study, all devices must be returned to the sponsor or the sponsor's designee. Ancillary supplies (i.e., CTG bands, isopropyl alcohol, mild detergent, ultrasound gel for CTG transducers) may not need to be returned.

6.2.2 APPEARANCE AND LABELING

The devices provided for this study will be labeled as investigational use only. Unique identifiers will be recorded to enable tracking of necessary device elements. Software versions used in the clinical study will be recorded.

7 STUDY DISCONTINUATION AND SUBJECT DISCONTINUATION/WITHDRAWAL

7.1 DISCONTINUATION OF M•WRAP APPLICATION/SUBJECT WITHDRAWAL

Subjects may withdraw from the study at any time. In the event that a subject experiences any adverse events, the protocol may be stopped, and the investigators will analyze the root cause. In addition, fetal wellbeing will be monitored and, if there are any effects considered to be the result of the study, the study may be stopped and there will be routine management of any subject if being seen in a clinical setting. If the subject is being seen in a non-clinic research setting, no CTG data will be interpreted and any adverse events requiring medical attention will be referred to the subject's physician. All adverse events will be followed with relevant records requested until resolution whenever possible. Each site investigator in a clinical setting will be responsible for determining appropriate clinical care. Site clinical staff may also make the decision to withdraw a subject for any other reason.

The reason for withdrawal/discontinuation should be recorded on the appropriate case report form (CRF). Data collected up to the point of withdrawal may be used.

8 STUDY ASSESSMENTS AND PROCEDURES

8.1 EFFICACY ASSESSMENTS

In order to assess efficacy, data will be collected simultaneously with both the M•wrap and CTG; this allows for a direct comparison of data obtained. CTG is considered standard of care and only that information will be used for clinical interpretation if the research is carried out in a clinical setting. The M•wrap data will not be shared with the practitioner or the subject and will not be used for any clinical interpretation or interventions. In the event the M•wrap location and position prevents CTG data acquisition necessary for care, the M•wrap will be removed, replaced, or repositioned. The study session will be stopped if standard of care cannot be achieved with the M•wrap in place.

8.2 SAFETY AND OTHER ASSESSMENTS

During the time any subject is wearing the M•wrap, safety will be monitored. In the clinical setting, a qualified site staff member designated as having appropriate clinical expertise will make determinations regarding appropriate clinical care and care will be provided for any adverse events. If adverse events occur in the non-clinical setting, subjects will be referred to a clinician for treatment as needed.

In the clinical setting, monitoring for fetal wellbeing with standard of care shall be continued. If the subject is being seen in a research visit setting, no interpretations will be made from CTG or the M•wrap.

8.3 ADVERSE EVENTS

8.3.1 ADVERSE EVENTS (AE)

Refer to section 10.6 for a list of adverse event terms and definitions.

Adverse events (AEs) will be monitored throughout the study period. All adverse events that occur during the time a subject is wearing the M•wrap will be collected and reported to Marani according to section 8.3.2. Potential AEs for this study are listed in the ‘Benefit/Risk Assessment’ in Section 2.3. Events or complications unrelated to the M•wrap system will not be collected after removal of the M•wrap device.

Since the study procedures are not greater than minimal risk, Serious Adverse Events (SAEs) are not expected. If any problems related to subjects do occur, these will be reported to the Institutional Review Board (IRB) in accordance with the local institution’s applicable policies and procedures.

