2.3 BENEFIT/RISK ASSESSMENT

This is a minimal risk study. The subjects in this study are not expected to be at any higher or additional risks than those who undergo cardiotocography (CTG) monitoring in clinic or hospital settings. There is minimal risk with CTG monitoring.

The M•wrap device employs electrocardiograph electrode sensors that are Food and Drug Administration (FDA) cleared. An electrocardiograph electrode is an electrode applied directly to the subject's skin to passively acquire and transmit the electrical signal at the body surface to a processor that produces an electrocardiogram (ECG) or vectorcardiogram. An electrocardiograph electrode is not intended to deliver

Confidential

Refer to QMS Number: **VAL-PRO-20-0004, Rev G**

DCR-00306, Effective – 14-Dec-2022

therapy to the subject, and information collected from the subject using the M•wrap will not be used to provide any treatment or treatment recommendations during the study. There is no personal benefit to the subject for taking part in this study. Subject benefit is limited to the understanding that they are contributing to research on a new device that may benefit others in the future.

The M•wrap is worn like tight-fitting compression clothing. Some people may view this as mildly uncomfortable. In addition, pressure artifacts on the abdomen or back are expected. Anticipated risks of the M•wrap system include but are not limited to known events associated with the use of ECG electrode systems and compression garments.

- Redness (erythema)
- Swelling (edema)
- Irritation
- Sensitization

Skin irritation will be carefully monitored before, during, and after the study session. Subjects will be immediately evaluated by the site investigator for any relevant unexpected skin irritation. Marani has designed the M•wrap to meet all applicable performance standards.

Privacy Protection: Acquired data from this study will be stored on HIPAA-compliant, encrypted servers. Only investigators, engineers, statisticians, and other study personnel involved in data recording and interpretation will be allowed access to these data.

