9.2.3 SAFETY OUTCOME MEASURES

Incidence of device related and/or protocol procedure related adverse events (AEs) related to the M•wrap study device.

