9.4.4 SAFETY MEASURES ANALYSIS

The incidence and overall counts and classifications of adverse events that are related to the M•wrap study device and/or protocol procedure will be summarized for the safety population. Summaries will

Confidential

Refer to QMS Number: VAL-PRO-20-0004, Rev G

DCR-00306, Effective – 14-Dec-2022

include incidence and counts overall for AEs and SAEs, by category, severity and by relationship to study device and /or protocol procedure.

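### After the wrap is removed, Section 8.3.1 keeps only M•wrap-related events, but the Section 9.4.4 safety analysis also counts events related to protocol procedures

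*Combined protocol and SAP*

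**What the plan says.** **Collection.** Section 8.3.1 has one rule for the period of wear and another for afterwards. During wear, relationship does not matter: "All adverse events that occur during the time a subject is wearing the M•wrap will be collected and reported to Marani". After removal, relationship to the wrap decides: "Events or complications unrelated to the M•wrap system will not be collected after removal of the M•wrap device". The same section opens with a general statement: "Adverse events (AEs) will be monitored throughout the study period". Section 2.3 adds, for skin: "Skin irritation will be carefully monitored before, during, and after the study session". Section 8.3.4 requires every AE to go on a CRF with its time of onset and sets no cut-off at removal. Section 8.2 speaks of safety monitoring only while the wrap is worn.

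**Grading.** Sections 8.3.3, 8.3.3.1 and 8.3.4 have staff record relationship to the device (or study application or product) and to protocol procedures as two attributes.

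**Analysis.** Section 9.4.4 states that "adverse events that are related to the M•wrap study device and/or protocol procedure will be summarized for the safety population", with summaries by either relationship.

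**Endpoint definition.** Section 9.2.3 reads: "Incidence of device related and/or protocol procedure related adverse events (AEs) related to the M•wrap study device". Section 3.4 has the same structure: "Incidence of device related and/or protocol procedure related adverse events (AEs) related to the study device, The Marani Health M•care System". The synopsis follows the 9.2.3 form.

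**The concern.** The safety outcome names two kinds of event, device-related and procedure-related. The rule that decides what is recorded after removal recognises only the first. The second kind can plausibly occur. Doppler and TOCO transducers are applied for the simultaneous recording, Section 6.2.1 lists ultrasound gel and CTG bands among the supplies, and Section 6.1 says "The black compression band will be placed over the M•wrap and the CTG transducers throughout simultaneous data collection". In research-only visits the CTG trace is not interpreted (Sections 4.1 and 8.2), so a reaction to a transducer or gel there arises purely from a study procedure.

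The 8.3.1 rule also makes staff decide whether an event is wrap-related before there is a record of it. Section 10.6 defines an AE regardless of relationship, and 8.3.3.1 asks for relationship to be graded for all AEs. An event screened out under 8.3.1 leaves nothing to audit, and a wrong decision can only reduce the count. Demonstrating safety is part of the stated objective (Section 3.1), and this is the only safety outcome.

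**Working it through.** No arithmetic applies. The plan attaches no figure to this point, and the documents give no event rate. The check sets the collection rule, the analysis rule and the endpoint wording side by side for each kind of event.

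| Event | Collected under 8.3.1? | Counted under 9.4.4? | Within the endpoint as worded in the synopsis, 3.4 and 9.2.3? |
|---|---|---|---|
| (a) Any AE that occurs during wear | Yes, whatever the cause | Yes, if related to wrap or procedure | Yes if related to the device; unclear if procedure-related only |
| (b) M•wrap-related, arising after removal | Not excluded | Yes | Yes |
| (c) Procedure-related, not M•wrap-related, arising after removal | Excluded | Yes | Unclear: named as a category, then limited to the study device |
| (d) Related to neither, arising after removal | Excluded | No | No |

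1. Rows (a), (b) and (d) show no conflict between collection and analysis. Row (c) does: 8.3.1 bars the event from collection and 9.4.4 counts it.
2. Row (c) is a category that the plan itself creates, because device and procedure relationship are graded separately and can differ.
3. The border between (a) and (c) depends on the onset date. Section 8.3.4 asks for time of onset, but no text says how to date a finding on skin that was covered until removal. One site could date it to wear and record it. Another could date it to removal, attribute it to a CTG transducer and leave it unrecorded. Both could point to the protocol.
4. The other statements do not settle row (c). Section 2.3 says skin is observed after the session, whereas 8.3.1 says what is collected. Section 8.3.4 has no cut-off and so disagrees with 8.3.1. Section 8.2 mentions monitoring during wear only.
5. The last column shows a second inconsistency that does not depend on the first. The synopsis, 3.4 and 9.2.3 name procedure-related AEs and then require them to be related to the study device. Read literally, a procedure-only event falls outside the endpoint but inside the 9.4.4 summary.

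**The case against.** A reader might infer something stronger: that procedure-related skin events first seen when the wrap comes off are lost from the endpoint, and that one could put a number on the loss. The documents do not support this, for five reasons.

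- During wear, the 8.3.1 test is when an event occurs, not when it is noticed. Redness from transducer pressure during the session occurred during wear and is collectable whatever its cause.
- An ambiguous mark need not drop out as a CTG effect. Section 8.3.3.1 judges on timing, its Potentially Related grade allows for other contributing factors, and Not Related requires a documented alternative cause. Section 2.3 lists redness, swelling and irritation as anticipated risks of the M•wrap system itself.
- No section says whether the black compression band is part of the M•wrap system, so reactions to it cannot be assumed to fall outside.
- Any count of missed events would rest on assumed rates for which the documents give no basis.
- The schema figures are not available here, so nothing can be said about whether a skin check at removal is scheduled.

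Two further arguments limit the point. Under the narrower wording of the synopsis, 3.4 and 9.2.3, the 8.3.1 rule largely matches the endpoint. And safety has no hypothesis test or success threshold, since Section 9.3 rests success on FHR and MHR.

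These arguments stand and confine the problem to row (c). They do not remove it. The during-wear reading of a mark found at removal is reasonable but is not written down for sites, and the match with the narrower endpoint holds only by setting 9.4.4 aside.

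**Conclusion.** The concern holds in a narrow form. A procedure-related AE that is not M•wrap-related, with onset after removal or dated to removal, may go uncollected under 8.3.1 although 9.4.4 would count it. The direction of any error is known, since it can only lower the AE count. Its size cannot be estimated from the documents. Separately, the safety endpoint has two definitions, one in the synopsis, 3.4 and 9.2.3 and a wider one in 9.4.4.

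This rests on a literal reading of 8.3.1 and on treating CTG transducers and gel as protocol procedures outside the M•wrap system. The safety analysis is descriptive, so the FHR, MHR and UC conclusions are unaffected. What is at stake is the completeness and cross-site consistency of the only safety outcome.

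**What to change.** 1. In Section 8.3.1, limit the post-removal exclusion to events unrelated to both the M•wrap system and the protocol procedures. Name the procedures meant (CTG transducers, gel, pulse oximeter) and say whether the black compression band belongs to the M•wrap system or to the procedures.
2. Add that a skin finding first seen at removal is recorded as occurring during wear and only then graded under 8.3.3.1.
3. Align the synopsis and Sections 3.4 and 9.2.3 with the 9.4.4 wording, so that the endpoint covers AEs related to the device, to a protocol procedure, or to both.

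The cost is a wording amendment, with no added visit. The downside is that the reported AE count may be slightly higher.
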